5.3 Secondary Objectives

The secondary objectives of this study are to:

- Compare the difference in BOE (urinary total NNAL, nicotine metabolites, S-phenylmercaptmic acid [S-PMA], blood carboxyhemoglobin [COHb], and exhaled carbon monoxide [CO]) and CPD between two methods for determining CPD during the Baseline Period:
 - Recall of average daily CPD for prior week using Past 7 Day Cigarettes Use Questionnaire (Day I).
 - Daily CPD tracking using an IVRS (7 day average of values recorded on Days 2 through 8).
- Compare the differences in percent change in urinary nicotine equivalent (NE), S-PMA, blood COHb, exhaled CO, and CPD from Baseline to EOS between adult smokers randomly assigned to Test Group (*ad libitum* VBM-FG2 use) and Control Group (no VBM-FG2).
- Compare the changes in all BOE and CPD from Baseline to EOS between Test Group and Control Group over 4 weeks.
- Characterize subgroups based on change in CPD from Baseline to EOS (no change, <50% reduction, ≥50% reduction, 100% reduction, increase) within each study group.
- Characterize subgroups based on change in total NNAL from Baseline to EOS (no change, reduction, increase) within each study group.
- Compare changes in the Fagerstrom Test for Cigarette Dependence (FTCD) from Baseline (Day 8) to EOS within and between each study group.
- Compare changes on the Quit Attempts and Quitting Intentions from Baseline (Day I) to EOS within and between each study group.

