Screening (Visit 1) will occur within 28 days of Day 1 (Day -28 to Day -1). An informed Consent Form (ICF) must be signed prior to conducting any study related procedures. Potential subjects will undergo an initial evaluation (vital signs, urine pregnancy test [females only], and questionnaires) to determine initial eligibility. If the subject passes the initial evaluation, then he/she will be provided with a sample of VBM-FG2 and asked to use the product as they like for 15 minutes. Subjects will then complete a Potential Purchase Interest Questionnaire. If they indicate that they "definitely would buy" or "probably would buy" the product on the questionnaire, then the subject will undergo the rest of the screening procedures (clinical labs and electrocardiogram [ECG]). Laboratory values will be evaluated by a local laboratory.

Subjects will return to the study site on the evening of Day 1 for Visit 2. A physical examination will be conducted and subjects who satisfy all the inclusion criteria and exclusion criteria will be eligible for enrollment in the study. Once a subject is enrolled in the study (Day 1), if they choose to no longer participate, they will be considered a drop-out/early termination subject.

During the Baseline Period, at Visits 2 and 3 (Days 1 and 8), blood and urine samples will be collected for analysis of BOE. Subjects will also complete the Past 7 Day Cigarettes Use Questionnaire while at the study site, to indicate their CPD over the previous week. During the Baseline Period (Days 1 to 8) subjects will report CPD daily through an IVRS.

At Visit 3, approximately 150 subjects will be randomized to either the Test or Control Group in a 3:2 ratio (with not more than a 60:40 distribution of either males or females to either group). VBM-FG2 will be dispensed to subjects randomized to the Test Group for *ad libitum* use beginning after the Day 8 IVRS.

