10. DEFINITION OF ANALYSIS POPULATIONS

Safety population includes subjects who have tried the test product during the study, including those subjects who participated only in the screening phase.

Intent to treat (ITT) population includes every subject who is randomized according to the randomization schedule.

Modified Intent to Treat (mITT) population includes every subject who has completed the baseline visit and has at least one post-baseline outcome measures.

Per-protocol population is defined as a subset of the ITT population, which is comprised of subjects who completed the study without any major protocol violations.

All protocol deviations that occur during the study will be considered for their severity and impact and will be taken into consideration when subjects are assigned to analysis populations. Details of subject assignment to the analysis populations will be listed.

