11.3.2 Secondary Endpoints

The secondary outcome measures or endpoints are:

- Differences in all BOE during the Baseline Period between Day 1 (weekly recall) versus Day 8 (daily tracking using IVRS).
- Difference in CPD during the Baseline Period between once weekly recall (Days 1 and 8) versus daily tracking (average of recordings on Days 2 through 8).
- Differences in the percent change from Baseline to EOS in BOE (urinary NE, S-PMA, blood COHb, exhaled CO) and CPD between the Test and Control Groups.
- Differences from Baseline to EOS in all BOE and CPD between the Test and Control Groups.
- Proporation of subjects in subgroups based on cigarette consumption change from Baseline to EOS (no change, <50% reduction, 50% reduction, 100% reduction, increase) within and between the Test and Control Groups.
- Proporation of subjects in subgroups based on total NNAL change from Baseline to EOS (no change, reduction, increase) within each group.
- Changes from Baseline (Day 8) to EOS in total scores of Fagerstrom Test for Cigarette Dependence (see Appendix 1), within and between the Test and Control Groups.
- Changes from Baseline (Day 1) to EOS on the Quit Attempts and Quitting Intentions, within and between the Test and Control Groups.

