Least squares mean and standard error for the product effect will be estimated by study group and visit with P-values. P-values will also be provided for other effects in Model 2. While group comparison will be made on multiple visits in the model, the difference in change from baseline to the last visit will be the primary comparison and other comparisons will be secondary.

The models will be applied on both the mITT and the Per-protocol populations.

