11.4.2 Statistical Analyses of Secondary Endpoints

Difference in baseline:

Paired T Test will be used to examine the difference in all 5 BOEs between Day 1 and Day 8.

Paired T test will also be used to examine the differences in CPD between the once weekly recall at Day 8 (from questionnaire) and the average daily tracking of CPD from Days 2 through 8 (from IVRS).

Difference in change from baseline:

Linear mixed model for repeated measures analyses of variance will be used for the analyses of the secondary outcome measures: percent change from baseline and absolute change from baseline in all other BOEs. The same model will be used for percent change from baseline and absolute change from baseline in CPD and Total score of FTCD, the model details are as follows:

For other BOEs:

Model 1:

Percent (or absolute) change from baseline = study group + visit+ study group*visit + subject + random error

Model 2:

Percent (or absolute) change from baseline = study group+ visit+ study group*visit + subject + CPD + sex + race + BMI + age + random error

For CPD and Total Score ofFTCD:

Model 1:

Percent (or absolute) change from baseline = study group+ visit+ study group*visit +subject+ random error

Model 2:

Percent (or absolute) change from baseline = study group+ visit+ study group*visit +subject+ sex + race + BMI + age + random error

where

CPD = fixed effect covariate representing average number of cigarettes per day for the past two days from IVRS

study group = fixed effect term (test or control)

sex = fixed effect (male or female)

age = fixed effect covariate (continuous)

race= fixed effect (White or Non-White)

BMI = fixed effect covariate (continuous)

visit= fixed effect term representing days (ordinal categorical variable)

subject = random effect

baseline = Day 8 value for BOE and average of Day 2 to 8 for CPD (IVRS)

If the study group*visit interaction term is not statistically significant (P-value > 0.10), then the interaction term will be removed from the model and all comparisons will be done using the overall product means. If the interaction effect is significant (P-value < 0.10), then the comparisons will be conducted for each study visit.

Least squared mean and standard error for the product effect will be estimated by study group and visit with p-values for statistical significance. P-value will also be provided for other effects in the model.

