All secondary and exploratory analyses will be conducted on the Per-protocol population only.

A linear regression analysis will be conducted within each group at each timepoint to examine the relationships between levels of all 5 BOEs (dependent variable) with either weekly cigarette counts (Day 1 and 8 from questionnaire) or daily cigarette counts (from IVRS) (independent variable). For total NNAL, the corresponding daily cigarette counts from IVRS will be the average of past 7 days. For other biomarkers, it will be the average of past 2 days. The regression analysis will be conducted on the Per-protocol population.

The proportion of subjects in subgroups will be provided with proportion and sample size based on:

- 1) Cigarette consumption change from Baseline (average of Days 2 to 8 from IVRS) to the last week (no change, <50% reduction, 2::50% reduction , 100% reduction, increase);
- 2) Total NNAL change from Day 8 to the last visit (no change, reduction, increase);
- 3) Total scores of FTCD change from Day 8 to the last visit (increase, no change, decrease)
- 4) Proportion of subjects in subgroups based on Changes from Baseline (Day 1) to EOS (increase, no change, decrease) on the change in Quit Attempts from Day 1 to last visit.
- 5) Proportion of subjects in subgroups based on Changes from Baseline (Day 1) to EOS (yes to no, no to yes, and same) on the change in Quitting Intentions from Day 1 to last visit.

The Mantel-Haenszel Chi-Square Test will be used for (1), (2), (3), and (4); Fisher exact test will be used for (5) to test the frequency differences between the two groups.

Additional statistical analyses:

Wilcoxon signed rank test will be used to test the FTCD score difference between the 2 baseline measures (Visit 2 and 3) for the test group. If there is no statistical significance, the average score will be related to the average amount of VBM-FG2 in the past week via linear regression. Otherwise the FTCD score for Visit 3 will be used.

For the test group only, a simple linear regression model will be used to examine the relationship between COHb and Exhaled CO at each post-baseline visit.

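### The secondary Test-versus-Control models for nicotine equivalents, S-PMA, COHb, exhaled CO and CPD use Per-protocol completers only; add an mITT analysis, as total NNAL already has

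*SAP*

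**What the plan says.** Section 5.3 makes the between-group comparison of percent changes a secondary objective, and names the measures and the Test side as follows: "urinary nicotine equivalent (NE), S-PMA, blood COHb, exhaled CO, and CPD from Baseline to EOS between adult smokers randomly assigned to Test Group". The comparator is the Control Group. Section 11.3.2 adds the change itself as a secondary endpoint: "Differences from Baseline to EOS in all BOE and CPD between the Test and Control Groups".

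Section 11.4.2 analyses the other biomarkers and CPD with a repeated-measures mixed model over Visits 4 to 7, and then fixes the population: "All secondary and exploratory analyses will be conducted on the Per-protocol population only".

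Section 10 defines the Per-protocol population as the part of ITT "which is comprised of subjects who completed the study without any major protocol violations". Its mITT population needs only a completed baseline visit and one post-baseline outcome.

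For total NNAL, Section 11.4.1 says: "The models will be applied on both the mITT and the Per-protocol populations". It adds that "the difference in change from baseline to the last visit will be the primary comparison and other comparisons will be secondary".

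On timing, Section 6 says: "At Visit 3, approximately 150 subjects will be randomized to either the Test or Control Group in a 3:2 ratio". Visit 3 is Day 8, and the trial is open-label.

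The Baseline Period comparisons are also secondary: "Paired T Test will be used to examine the difference in all 5 BOEs between Day 1 and Day 8". A second paired test sets CPD recalled at Day 8 against the IVRS average for Days 2 to 8.

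**The concern.** Randomisation makes the groups comparable as assigned. Whether a subject completes, and whether a violation occurs after Day 8, is settled after assignment, in an open-label trial in which only one group receives the product. Reasons for leaving can therefore differ by group. Violations at screening or in the Baseline Period come before assignment, and excluding those subjects does not by itself unbalance the groups. The selection is thus partly, not wholly, post-randomisation.

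Three things follow for nicotine equivalents, S-PMA, COHb, exhaled CO and CPD:

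- The comparison may be biased, by an amount the plan gives no means of judging, because the mITT versus Per-protocol contrast is planned only for NNAL.
- A subject who leaves after Visit 5, say, contributes nothing, although the mixed model can use those values without imputation and so within the no-imputation rule of Section 11.1.
- The primary biomarker and the other biomarkers are reported on different sets of subjects.

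The paired baseline tests are a smaller matter. Their data are complete by Day 8, yet a subject who leaves in week 4 is removed. These tests serve one of the two purposes in Section 5.1, the choice of CPD reporting method.

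**Working it through.** **Plan's own figures.** The 3:2 split of 150 gives 150 × 3/5 = 90 Test and 150 × 2/5 = 60 Control, as Section 6 states. Section 8 gives no effect size, SD, power or dropout rate. There is no stated figure to dispute, and every exclusion rate and outcome gap below is an assumption.

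**Step 1: populations side by side.**

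| Analysis | Population(s) |
|---|---|
| NNAL mixed models (Section 11.4.1) | mITT and Per-protocol |
| Nicotine equivalents, S-PMA, COHb, exhaled CO and CPD mixed models (Section 11.4.2) | Per-protocol only |
| Paired Day 1 to 8 comparisons (Section 11.4.2) | Per-protocol only |

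**Step 2: size of a possible bias.** Let d be the share excluded in a group and g the mean outcome of the excluded minus that of the retained, in SD. The retained mean differs from the full group mean by d × g, so the group difference is off by b = d_T × g_T − d_C × g_C. With the same d in both groups, SE = sqrt(1/(90(1−d)) + 1/(60(1−d))). The chance of a false-positive result at the 5% level is P(|Z + b/SE| > 1.96).

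- 10% excluded: 81 and 54 remain, SE = 0.176. With g = 0.5 in Test only, b = 0.10 × 0.5 = 0.05 SD and the error is 5.9%. With g = 1, b = 0.10 SD and the error is 8.8%.
- 20% excluded: 72 and 48 remain, SE = 0.186. With g = 0.5 in Test only, b = 0.20 × 0.5 = 0.10 SD and the error is 8.4%. With g = 1, b = 0.20 SD and the error is 18.9%.
- Equal d and g in both groups: b = 0 and the error is 5%.

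**Step 3: would mITT help?** A simulation with 90 and 60 subjects, four visits, an assumed within-subject correlation of 0.6 and no true effect let subjects leave after Visits 4 to 6, and tested the groups at Visit 7. Losses were 10% and 20%.

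- Leaving depends on the last observed value in Test only (logit slope 1.5 per SD): error with completers only 8.4% and 14.3%; with mITT 5.5% and 5.3%. Known variances in place of REML gave 7.1% and 12.5% for completers, and 5.2% and 4.9% for mITT.
- The same selection in both groups: completers only 4.8% and 5.9%; mITT 4.7% and 5.2%.
- Leaving depends on the subject's unobserved level in Test only, with some leaving before Visit 4: at 20% loss the Visit 7 bias is 0.17 SD with completers only and 0.09 SD with mITT, so about half remains.

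Only dropout was simulated, not exclusion for violations.

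**Step 4: data discarded.** The plan yields 150 × 4 = 600 post-baseline values per biomarker. If all of the 10 or 20% excluded are leavers, that is 15 or 30 subjects. With about two values each before leaving, about 30 or 60 collected values go unused.

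**Step 5: paired baseline tests.** The 95% half-width is 1.96/sqrt(n), in SD of the paired difference: 0.160 for n = 150, 0.169 for n = 135 (10% excluded) and 0.179 for n = 120 (20% excluded). The widening is sqrt(150/135) = 1.05 and sqrt(150/120) = 1.12, or 5% and 12%.

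**The case against.** The strongest reply is that this is a pilot meant to estimate the variability of NNAL change, that the primary comparison already has an mITT analysis, and that Section 11.1 lists data for all subjects up to withdrawal. The bias needs selection that differs by group, and nothing in the SAP says it will. With equal selection the completers' analysis keeps its error rate. All this stands. It limits the weight of the point but does not remove it, because Section 11.4.2 still prescribes between-group p-values for these endpoints and plans no analysis that would show whether exclusion mattered.

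The mITT set is not a full remedy. It needs one post-baseline value, and its near-nominal results in Step 3 come from leaving that depends on observed values, where a likelihood model is expected to do well.

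A reader might infer that Sections 11.4.1 and 11.4.2 contradict each other on NNAL, since the former calls comparisons other than the last visit secondary and the latter sends every secondary analysis to Per-protocol, so that the population could be chosen after the data are seen. The text does not go that far. Section 11.4.1 fits both percent and absolute change in NNAL on both populations, one fit yields every visit, and the mixed models of Section 11.4.2 are for the other biomarkers. What remains is an unstated scope.

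Nor does the reference to random assignment in Section 5.3 contradict Section 11.4.2. It says how the groups are formed and names no analysis population.

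**Conclusion.** The point holds for the five mixed-model comparisons. Restricting them to completers without major violations conditions a randomised comparison partly on later events and discards usable data, while an mITT set is already required for NNAL. The change is worth making but is not critical.

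The text supports a risk of bias, not a demonstrated one. At an assumed 10 to 20% exclusion and a 0.5 SD gap in Test only, the risk amounts to 0.05 to 0.10 SD and a two-sided error of 5.9 to 8.4%. A larger one-sided gap gives more, and equal selection gives none. Confidence is high on what the plan says and low on the size.

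For the paired baseline tests the demonstrable cost is precision, with intervals about 5 to 12% wider at the same assumed rates. A reader might infer bias there too, but the documents do not show it. The overlap on NNAL needs a clarifying line only, and the primary comparison at the last visit is untouched.

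**What to change.** Keep the existing sentence in Section 11.4.2 as the default, so that no analysis is left without a population, and add after it:

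> Exceptions: (a) The mixed models for percent and absolute change in nicotine equivalents, S-PMA, COHb, exhaled CO and CPD will be fitted on the mITT population using all available post-baseline values (lead analysis) and on the Per-protocol population (sensitivity analysis). (b) All NNAL mixed-model comparisons, including absolute change and visits other than the last, follow the populations in Section 11.4.1. (c) The Day 1 to 8 paired comparisons of BOE and CPD will use all randomised subjects with both measurements.

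The category tests, FTCD, the quit measures and the exploratory regressions stay on Per-protocol. FTCD and the quit measures have only Day 36 as their post-baseline visit (Section 11.2), so mITT would add little. The category tests rely on the last visit or EOS, and Section 6 allows the EOS visit to be an early termination visit; moving them to mITT would first need those terms defined.

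The cost is a few more tables on a set that must be built anyway. If leaving depends on unobserved values, part of the bias remains, and the report should say so.

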5. PURPOSE AND STUDY OBJECTIVES

5.1 Purpose

The purpose of this study is to:

- Estimate the change in biomarkers of exposure (BOE) in adult smokers using VBM-FG2 versus adult smokers not using VBM-FG2.
- Determine the appropriate cigarettes per day (CPD) reporting method for baseline measurements (for interactive voice response system [IVRS] Base line is defined as the average CPD recorded on Days 2 through 8).

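### Comparisons that use only Day 1 to Day 8 data are restricted to the Per-protocol population, so complete baseline pairs are dropped for later events

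*SAP*

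**What the plan says.** Section 5.1 gives two purposes. The second is to "Determine the appropriate cigarettes per day (CPD) reporting method for baseline measurements". Section 5.3 makes it the first secondary objective, comparing biomarkers and "CPD between two methods for determining CPD during the Baseline Period".

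Section 11.4.2 sets the tests. For biomarkers, "Paired T Test will be used to examine the difference in all 5 BOEs between Day 1 and Day 8". For cigarettes per day (CPD), a paired t test examines "differences in CPD between the once weekly recall at Day 8 (from questionnaire) and the average daily tracking of CPD from Days 2 through 8". The section also plans regressions of each biomarker on cigarette count, within each group at each timepoint; those at Day 1 and Day 8 belong to the same question.

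For the analysis set, section 11.4.2 says "All secondary and exploratory analyses will be conducted on the Per-protocol population only", and it repeats the Per-protocol restriction for the regressions. Section 10 defines that population as the part of the ITT (randomised) population "comprised of subjects who completed the study without any major protocol violations". Under section 6 the Baseline Period closes with the Day 8 IVRS call, assigned product is used only after that call, and the study runs to Day 36. Of subjects enrolled on Day 1, section 6 says that "if they choose to no longer participate, they will be considered a drop-out/early termination subject".

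**The concern.** The paired tests compare two ways of measuring the same person before assigned product is used, and the Day 1 and Day 8 regressions use the same period. Once the Visit 3 samples, questionnaire and IVRS calls are in, nothing that follows can change those values. Membership of the analysis set nevertheless depends on the next four weeks. A subject with complete baseline data is removed for withdrawing in that time, for a major violation after Visit 3, or for leaving at Visit 3 without being randomised.

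Two things are at stake. One is precision, lost without any gain in validity. The other is selection: those kept are the subjects who went on to complete four more weeks of daily calls and weekly visits, and that behaviour may be related to how they report cigarettes. No second analysis set is planned for these comparisons, so the report would not show whether the restriction mattered.

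**Working it through.** **What each analysis needs and what the plan requires**

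| Analysis (section 11.4.2) | Last data used | Required by the Per-protocol rule |
|---|---|---|
| Paired t test, five biomarkers | Day 8 | Randomised, study completed, no major violation |
| Paired t test, recall against IVRS | Day 8 | Same |
| Biomarker-on-CPD regressions at Day 1 and Day 8 | Day 8 | Same |

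Section 10 attaches no day number to completion. Day 36 follows from the schedule in section 6, which classes those who leave earlier as early terminations. No other section exempts the baseline comparisons. Section 11.4.1 adds the mITT population for the primary models only.

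**Inputs.** About 150 subjects are randomised, 90 Test and 60 Control (section 6). The SAP gives no standard deviation, effect size, power, drop-out rate or violation rate, so it has no figure to reproduce. Let *d* be the share of subjects with complete baseline data who are not Per-protocol. Every value of *d* below is an assumption.

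**Precision.** Pairs lost = 150 × *d*. With the same standard deviation in kept and dropped subjects, the standard error is multiplied by 1/√(1 − *d*).

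| Assumed *d* | Pairs lost | Pairs kept | Standard error ratio |
|---|---|---|---|
| 5% | 7.5 | 142.5 | 1/√0.95 = 1.026 |
| 10% | 15 | 135 | 1/√0.90 = 1.054 |
| 20% | 30 | 120 | 1/√0.80 = 1.118 |
| 25% | 37.5 | 112.5 | 1/√0.75 = 1.155 |
| 30% | 45 | 105 | 1/√0.70 = 1.195 |

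To put this in terms of power, take a standardised paired difference that 150 pairs would detect with 80% power at a two-sided 5% level: (1.960 + 0.842)/√150 = 0.229. Power with *n* pairs is about Φ(0.229√*n* − 1.960). That gives 75.7% at 135 pairs, 70.7% at 120 and 65.0% at 105. The effect size is chosen only for illustration.

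The base of 150 counts randomised subjects. Anyone enrolled on Day 1 with complete baseline data but never randomised is a further loss, and the SAP does not give their number.

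**Selection.** The Per-protocol mean differs from the mean in all subjects by *d* × (mean in those kept − mean in those dropped). Take *d* = 20% and a recall-minus-IVRS difference of 1 CPD in those kept:

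- 3 CPD in those dropped: all-subject mean 0.8 × 1 + 0.2 × 3 = 1.4, so the planned 1.0 is too low.
- 1 CPD in those dropped: all-subject mean 1.0, so no bias.
- −1 CPD in those dropped: all-subject mean 0.8 × 1 + 0.2 × (−1) = 0.6, so the planned 1.0 is too high.

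A gap of 2 CPD thus moves the estimate by 0.4 either way at 20%, and by 0.2 at 10%. The SAP does not say which case applies.

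**The case against.** Per-protocol is a defensible set for an exposure pilot, and a single set keeps the secondary tables consistent. That argument suits the Test-against-Control models, where adherence to the assignment bears on the effect. It does not carry over to a comparison finished before assigned product is used.

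The loss may be small. This stands: at 5 to 10% exclusion the standard error rises by only about 3 to 5%. Data up to withdrawal are listed (section 11.1) and supplementary analyses are allowed (section 4), so nothing is irrecoverable. A listing or a later analysis is still no substitute for a prespecified set.

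Three stronger readings are tempting, and the SAP does not support them.

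- *A reader might infer that the restriction understates the difference between the methods.* The paired t test concerns a mean difference. Poorer agreement among those dropped could be wider scatter around the same mean, or errors of opposite sign. Nothing in the SAP shows that completers report more consistently.
- *A reader might infer that the mITT population would not help.* It would recover most later drop-outs. A subject who stops on Day 20 would normally have been sampled at Visit 4 (Day 15 ± 1) and so have the post-baseline measure that section 10 asks for. The mITT population misses only those with no post-baseline measure.
- *A reader might infer that the method would be judged in people unlike those entering the pivotal study.* The SAP mentions that study but gives neither its eligibility criteria nor its analysis sets.

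A further objection bears on the remedy. Taking everyone with two values would admit subjects with a major violation during Days 1 to 8. It also would not fit regressions run within study group, because a subject who is never randomised has no group. Both points stand, and the fix allows for them.

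**Conclusion.** The point holds for the baseline-period paired tests and the Day 1 and Day 8 regressions, and only for those. As written, section 11.4.2 discards complete Day 1 to Day 8 data because of events after Visit 3 that cannot affect them, in a comparison serving one of the study's two purposes.

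The certain cost is precision: about 5 to 15% on the standard error if 10 to 25% of subjects are not Per-protocol, and less if attrition is low. That range is assumed, and it takes equal variability in kept and dropped subjects. The selection effect is a possibility to guard against; neither its size nor its direction can be obtained from the SAP. This is a modest problem in a pilot, worth correcting because correction costs very little.

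**What to change.** In section 11.4.2, limit the Per-protocol sentence to the other secondary and exploratory analyses, and set the baseline-period analyses as follows:

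- **Paired tests (biomarkers and CPD):** all enrolled subjects with both values for that measure and no major protocol violation during Days 1 to 8, whatever happens later.
- **Day 1 and Day 8 regressions within group:** all randomised subjects with the biomarker and CPD values at that timepoint, under the same Day 1 to 8 violation rule.
- **Supportive:** the Per-protocol versions of both, so that any effect of the restriction can be seen.

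Section 11.2 averages whatever IVRS calls are available from Days 2 to 8, so even one call yields a value. Whether very sparse reporting counts as a major violation should be settled when deviations are classified.

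The cost is a few lines in the SAP, population flags for these analyses and the extra supportive tables. No new data are needed. The small downside is that the sample size in these tables will differ from the other secondary tables, which a footnote can explain.
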